#### 10.3 Analysis

As above

#### 11. Trial Steering Committee (TSC)

The Trial Steering Committee will consist of;

- Chief Investigator and co-investigators [name], [name], [name], [name]
- Research staff conducting the study
- Independent Chairman [name]
- Statistician [name]
- Endomagnetics Scientific Representative.

The function of the committee is to ensure ongoing safety of the study to patients and to monitor ongoing efficacy of the device. The committee will convene after three months to review the primary end-point and to discuss the safety of the Study, and to discuss recruitment.

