# **Role of Sponsor and Funder**

Manchester University NHS Foundation Trust is acting as sponsor for this study and is assuming overall responsibility for the initiation and management of the

Title: Costs and benefits of Magtrace® in breast surgery Protocol V1 Date 03/08/2022

IRAS 293053 Page 2 of 45

study. The Trust will provide permission to conduct the research and monitor the progress of that research. The research team all hold substantive or honorary contracts with the Trust and therefore the sponsor has influence over all aspects of the study design, conduct, data analysis and interpretation, manuscript writing, and dissemination of results which are the responsibility of the research team.

The funder Endomagnetics Ltd have provided funding to conduct the trial, reviewed the study design, a representative will sit on the trial steering committee and be sent a copy of the results at the end of the trial.

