#### Safety Oversight:

The Trial Steering Committee (TSC) will meet once all patients have completed the study or earlier if considered necessary by the Chief Investigator. They will consider all Serious adverse events and adverse events and the main safety and efficacy outcomes.

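### The three-month steering committee review of the primary endpoint is not limited to pooled data, although recruiters, timing staff and the funder sit on the committee

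*Protocol*

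**What the plan says.** Section 11 fixes the date and agenda of a meeting: "The committee will convene after three months to review the primary end-point and to discuss the safety of the Study, and to discuss recruitment". It also gives the committee the task "to monitor ongoing efficacy of the device". Besides an independent chair and a statistician, the members are the chief investigator and co-investigators, "Research staff conducting the study" and the "Endomagnetics Scientific Representative".

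Section 9, under Safety Oversight, gives another schedule: "The Trial Steering Committee (TSC) will meet once all patients have completed the study or earlier if considered necessary by the Chief Investigator". The main safety and efficacy outcomes are to be considered then.

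The statement on the role of sponsor and funder says of the funder that "a representative will sit on the trial steering committee and be sent a copy of the results at the end of the trial".

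Section 4.1 defines the primary endpoint as the cost effectiveness of Magtrace compared with Technetium, from Part 1. Under Study design (Part 1) in Section 4.2, research staff consent patients, shadow them and time them with a stopwatch, about 20 per group. The recorded resource use is then multiplied by unit costs.

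**The concern.** A cost-effectiveness comparison has no content until the arms are set against each other. A committee that reviews it at three months would see comparative data unless something restricts what is shown, and the Protocol contains no such restriction.

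Most of the committee are people whose later conduct could shift the result. Investigators and research staff approach and consent patients, surgeons and their teams arrange the lists, and research staff hold the stopwatch. The endpoint rests on minutes recorded by observers who know the allocation. Someone who has seen that one pathway looks cheaper may, without intending to, start or stop the clock differently, schedule differently, or present the study differently to the next patient. Such bias cannot be detected or removed afterwards.

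The funder makes the device under test. A cost study is more open to criticism if its funder saw comparative results while data were still being collected.

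**Working it through.** The Protocol gives no figure for this review, so the check is mainly a comparison of the text.

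1. **What is reviewed.** Section 11 names the primary endpoint, and Section 4.1 defines it as one tracer compared with the other. The quantity is between-arm by definition.

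2. **Who reviews it.** Section 11 lists the investigators, the staff conducting the study and the funder's representative. Section 4.2 has research staff consenting and timing patients, and Section 5.1 has a consultant breast surgeon or research nurse taking consent. Recruiters and timing staff are therefore on the committee or drawn from the groups that are.

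3. **Whether they know the allocation.** Section 6.1 has the operating surgeon inject Magtrace, and staff shadow each patient. No blinding is described anywhere. That the study is open-label is inferred from these procedures; the Protocol does not use the term.

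4. **What limits the review.** No section mentions pooled data, a closed session, or a rule for acting on what is seen.

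5. **How the schedules compare.**
 - Section 11: a fixed meeting at three months, with the primary endpoint on the agenda.
 - Section 9: the committee "will meet once all patients have completed the study or earlier if considered necessary by the Chief Investigator".
 - A three-month meeting is allowed under Section 9 but not required by it. Someone working from Section 9 alone would plan no meeting during the trial.

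6. **How much data collection could follow.** The accrual window for Part 1 is not stated, nor is the date from which three months runs. The study summary gives 14 months in total for both parts, and 3/14 = 21%. For illustration, assume that the 40 main-phase patients accrue evenly over 6 to 14 months, with three months counted from the first patient:
 - Randomised by the review: 40 × 3/6 = 20, down to 40 × 3/14 = 8.6.
 - Still to be randomised: 40 − 20 = 20, up to 40 − 8.6 = 31.4.
 - Completed, with participation of 4 to 8 weeks (0.92 to 1.84 months at 4.345 weeks per month): at most 40 × (3 − 0.92)/6 = 13.9, at least 40 × (3 − 1.84)/14 = 3.3.

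Under these assumptions half or more of the patients would be recruited and timed after the review, and the review itself would rest on about 3 to 14 completed patients.

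**The case against.** The strongest objection is that Section 11 never mentions arms, a comparison or a test. Section 4.2 places the costing after 20 patients per group have been observed, and Section 15 sends the final data set to the external statistician for the economic analysis. The three-month item could mean only a check on how the endpoint is being captured. That reading is possible, but the words do not secure it: the item is the primary endpoint itself, next to a remit to monitor efficacy. If a capture check is meant, the fix simply says so.

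A second objection is that timing staff already know each patient's tracer and see the differences at first hand, so withholding a summary cannot blind them. This stands, and it limits what the fix can achieve. An aggregated cost difference is still more than any one observer sees, and investigators and the funder do not see every patient.

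Three stronger readings are tempting, and the documents do not support them:

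- **The two meeting schedules contradict each other.** Section 9 allows earlier meetings at the chief investigator's discretion, so both can be followed. Nor is the trial without safety oversight: Section 5.6 has the chief investigator monitoring safety, and Section 9.1 requires immediate reporting of serious adverse events.
- **The funder statement is breached.** It says that results are sent at the end, not that nothing is seen before then. The tension is by implication only.
- **The type I error rate is inflated.** Part 1 states no test, significance level or stopping rule. Any inflation figure would rest on a procedure that the Protocol does not contain, so none is given here.

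**Conclusion.** The point holds as one of exposure to operational bias. Followed as written, Section 11 allows comparative interim results on a staff-measured endpoint to reach those who recruit and time patients, and the funder, with no rule on their use. The two meeting schedules are compatible but should be aligned.

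The size of any bias cannot be derived from the documents. The number of patients affected depends on the accrual window: about 20 to 31 of 40 under the assumptions above, and fewer if accrual were faster than six months. The conclusion rests on two inferences: that reviewing cost effectiveness means seeing data by arm, and that the trial is unblinded. Both follow from the Protocol's definitions and procedures, although neither is stated outright. The point deserves correction before recruitment starts, but it does not invalidate the design.

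**What to change.** **Section 11.** Reword so that the three-month meeting covers safety, recruitment and data completeness only. Add that no comparative summaries by arm of cost, time or other efficacy outcomes go to investigators, timing staff or the funder until Part 1 data collection is complete and the database is locked. Word the committee's efficacy-monitoring task to match, and state the date from which the three months run.

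**Section 9, Safety Oversight.** List the three-month safety and recruitment meeting alongside the end-of-study meeting, keeping the chief investigator's option to call others.

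Reporting of serious adverse events under Section 9.1 stays as it is. The restriction must not be worded to cover all data by arm, because the chief investigator receives every such report.

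The cost is wording in two sections and a short completeness report for the meeting. Sample size, visits and data collection do not change. The change lessens the bias but cannot remove it while the observers know the tracer.

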#### 12. Direct Access to Source Data and Documents

The Investigator(s) will permit trial-related monitoring, audits, REC review, and regulatory inspections by providing the Sponsor(s), Regulators and REC direct access to source data and other documents (e.g. patients' case sheets, X-ray reports, histology reports etc.), in line with participant consent.

# 13. Ethics and Regulatory Approvals, Amendments and Reports.

Before the start of the study, a favourable opinion will be sought from an NHS Research Ethics Committee (REC) for the study and all the supporting documents including the protocol, information sheets, informed consent forms and other relevant documents. The study team will be responsible for the maintenance of a study site file, in which all current and superseded study documents will be retained. Also contained in the site file will be the approval documentation including correspondence with relevant authorities such as the HRA and REC.

The study team are responsible for producing progress reports throughout the study, including an annual progress report (APR) which will be submitted to the REC within 30 days of the anniversary date on which the favourable opinion was given, and annually until the trial is declared ended. The Chief Investigator will notify the REC of the end of the study, and will submit a final report with the results, including any publications/abstracts, to the REC within 12 months of the end of the study. If the study

Manchester University

NHS Foundation Trust

is ended prematurely, the Chief Investigator will notify the REC, including the reasons for the premature termination.

During the life of the study, there may be amendments to the study protocol and/or documentation. Substantial amendments will not be implemented until NHS REC review is in place and local approvals have been obtained.

No participants will be enrolled into this research study prior to the study being reviewed by the relevant regulatory authorities and receiving HRA and REC approvals, as well as approval from the R&I office at Manchester University NHS Foundation Trust. All correspondence including amendments with the REC will be retained in the Trial Master File.

# 14. Quality Control

Monitoring of this trial will be to ensure compliance with Good Clinical Practice and scientific integrity will be managed and oversight retained, by [name] and the Trial Steering Committee, as per the study monitoring plan. Data will be evaluated for compliance with the protocol and accuracy in relation to source documents. Following written standard operating procedures, the monitors will verify that the clinical trial is conducted and data are generated, documented and reported in compliance with the protocol, GCP and the applicable regulatory requirements.

There is a requirement for the maintenance of an updated training record for each member of the research team and retention of GCP training certificates.

The study will be subject to the audit and monitoring regime of Manchester University NHS Foundation Trust in line with applicable MFT SOPs and policies. The study will have, as a minimum, an annual survey sent out for completion by a member of the research team.

#### 15. Data Handling and Management

The Chief Investigator will act as custodian for the trial data. The following guidelines will be strictly adhered to:

Patient data will be pseudonymised using a study code that is linked to the recruitment log

All pseudonymised data will be stored on a password protected computer within MFT;

Anonymised data will be transferred to Nexus Clinical Analytics for health economics analysis by Encrypted email.

All data will be kept strictly confidential according to Good Clinical Practice (GCP) Guidelines. All identifiable data will be stored by the Manchester University NHS Foundation Trust in a secure fashion for 10 years after completion of the study in accordance with the ICH GCP. Source data for the trial are the consent form, Case Report forms and patients' medical notes. The trial data and documentation will be archived as per the MFT archiving SOP.

Excel spreadsheets used for the study, including the recruitment log, will be saved under a study folder that will be permissions based as to who can amend and view the data within the study team. Each excel spreadsheet containing patient identifiable data will be password protected. If any changes are made to the excel spreadsheets by the CI, then a new iteration of the excel form will be saved each time any changes are made. These will be named with the date of the update and the name of the team member who made the change and saved. In the properties section of the saved Excel file, the created, accessed and modified dates will all be the date of the update. The file will not be modified in any way after they have been saved. A new iteration will be created for live data. The spreadsheets will be updated and maintained by the research practitioner.

These will be stored on Trust encrypted password protected devices within MFT. Data on the trust servers is backed up continuously and at the end of each day. If data is lost, data will be recovered via the trust IT department back up service for data stored on the share drive.

The final data set will be fully anonymised including removal of study code prior to being transferred to [name], Statistician, Nexus Clinical Analytics for health economics analysis by Encrypted email. The final trial data set will be shared with authorised representatives at Manchester University NHS Foundation Trust, members of the Trial Steering Committee and Endomagnetics

# 15.1 Data Management

The CRF will be developed by the CI and trial steering group (TSC). CRFs will be treated as confidential documents and held securely in accordance with regulations. The investigator will make a separate confidential record of the participant's name, date of birth, local hospital number or NHS number, and Participant Trial Number (the Trial Recruitment Log), to permit identification of all participants enrolled in the trial in accordance with regulatory requirements and for follow-up as required. Completion of CRFs shall be restricted to those personnel approved by the Chief Investigator or designated deputy and recorded on the 'Trial Delegation Log'. All paper forms shall be

Manchester University
NHS Foundation Trust

filled in using black or blue ballpoint pen. Errors shall be crossed out (but not obliterated by using correction fluid) and the correction inserted, initialled and dated. Corrections should be made legibly and initialled and dated by approved personnel. The reasons for significant changes must be provided. If any data are not available, omissions should be indicated on the case report forms. The NHS Code of Confidentiality will be followed for this study.

# 16. Publication Policy

The study data will be presented at national and international conferences and published in a peer reviewed journal. The Chief Investigator will have rights to publish the trial data with a fully anonymised data set.

Participants will be able to indicate on the consent form if they wish to receive a summary of the study results either by email or in the post.

MFT is the owner off all data sponsored at MFT. This research will be registered on the Clincaltrials.gov clinical trial registry as will a summary of the study results.

# 17. Insurance / Indemnity

The NHS indemnity scheme will apply to this study to ensure it meets the potential legal liability of the sponsor, equipment, employer and investigators/collaborators for harm to participants arising from the management, design and conduct of the research. No arrangements will be made for the payment of compensation in the unlikely event of harm.

## 18. Financial Aspects

Funding to conduct the trial is provided by Endomagnetics Ltd, [name].

